## 9.8 Quality control

A pre-test of the questionnaire will be performed to ensure its comprehensibility and consistency (see section 9.4).

Suazio will follow its procedures for quality control during the conduct of the survey, which includes but is not limited to:

- Randomization of answer options
- Consistency checks for plausible data
- Checks for completeness of data and perform follow-up as needed

Medtronic BioPharma will follow Medtronic BioPharma procedures and study specific plans will be followed for quality control, which includes but is not limited to:

- Documenting all statistical analysis programs used, including version number
- Archiving the original database and any derived data sets, and all relevant study documents in an electronic document system

#### 9.10 Limitations of the research methods

Potential limitations to using this online survey include:

- Non-response bias: This is an inherent limitation in the survey study design. The non-response rate is reduced through the use of a telephone screening, short survey and the potential for compensation for time.
- Social desirability response bias: Surgeons may respond positively rather than truthfully. In order to reduce the probability of this type of bias, surveys are anonymous, questions are not leading, and are designed to elicit truthful responses.
- Sample is not random: A random sample of individuals meeting the selection criteria equalises the potential for bias to occur, making the sample potentially useful for generalising to the overall population. However, the small number of potential surgeons who would meet the selection criteria effectively removes the potential for randomisation.
- Self-selection bias: Even with the selection criteria it may be only the most motivated, experienced or engaged surgeons who participate leading to artificially high rates of awareness. This is reduced by decreasing the non-response bias, see above. Furthermore, the sample is chosen from all current users in the countries, regardless of quantity of InductOs provided in the past years.

These limitations are acknowledged and, given the nature of the data collected, should not greatly impact the conclusions drawn from the data collected from respondents. Efforts, where possible, will be made to address and reduce the impact of these limitations, see bullets above.

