## 9. Research methods

#### 9.1 Study design

This study is a cross-sectional cohort analysis of InductOs-using spine surgeons to establish:

• their current level of knowledge regarding heterotopic ossification,

 the current level of knowledge, and degree of access to or utilisation of educational materials about the potential for post-surgical heterotopic ossification and practical risk minimisation measures.

A cross-sectional cohort study methodology was judged to be appropriate to meet the expectations of the European Medicines Agency (EMA) based on:

- The nature of the medicinal product: single use implantation in a relatively small target population
- The nature of heterotopic ossification which is not an uncommon adverse event of many orthopaedic procedures and it does not always manifest clinically
- The lack of appropriate data fields captured in the national spine registries across Europe,
- The period over which the educational materials have been available (since summer 2017)

The cohort study will be composed of an anonymous, online survey (see Annex 3) with the aim of answering the study questions outlined in section 8.

The screening for eligibility and online interviews will be conducted in the surgeon's native language. All materials will be prepared using the English master questionnaire as the baseline (see Annex 3). Translations will undergo appropriate quality checks prior to sign off by the research team.

The researchers will secure responses from 55 individuals from the four selected countries split proportionally based on usage, see section 9.5.

A pilot project of 2 surgeons will test the survey for clarity and accuracy of response and translated materials in an iterative manner. If no changes are made, then the pilot recruits will be included in the main cohort.

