#### Exclusion criteria

Participants meeting any of the following criteria will not be included in the study:

- 1. Physicians that participated in the testing of this survey, if there are substantial changes made to the survey post-pilot i.e. changes which, in the view of the research team, make the participants contributions invalid or potentially compromising of the study objectives
- 2. Physicians that either themselves work for or have immediate family members who work for Medtronic, third parties involved in this study, or a regulatory agency (EMA, MHRA, HPRA, ANSM, BfARM)

During the initial phone call, screening questions will be asked to determine the eligibility of the physician for participation.

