## 9.5 Study size

The minimum sample size needed to obtain a proportion with confidence interval with the lower limit above the 80 % minimum awareness was calculated. For this calculation an alfa of 0.05 with a two-sided interval and a distance from proportion to limit of 0.1 was used with the expected proportion of 90 %. This leads to a minimum sample size of 35.

To ensure inclusion of data from the different participating countries, this study aims at collecting responses from physicians covering roughly 10 % of purchasing pharmacies that have received InductOs in the past 2 years in each target country. However, if a greater number of respondents complete the questionnaires for a given target group, these responses will be integrated into the analyses.

The following number of completed surveys are planned per country:

France: 15Germany: 15

- United Kingdom: 15

- Ireland: 10

This brings the total to 55 completed surveys which is above the calculated minimum sample size. Taking into account response rate of roughly 60 % and screening failures an estimated 120 surgeons will be screened for eligibility.

Recruitment rate will be monitored by the researchers; and if it becomes apparent that the there is a risk of the study not meeting the recruitment target then other countries with InductOs sales will be included in the study to widen the pool of potential participants. In the selection of additional countries for recruitment, priority will be given to countries where the existing translated materials are used.

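### Section 9.10 dismisses an upward self-selection bias without support, although the plan expects about 60 % response and analyses completers only

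*Protocol*

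**What the plan says.** On self-selection, Protocol 9.10 says that "it may be only the most motivated, experienced or engaged surgeons who participate leading to artificially high rates of awareness". It relies on measures that lower non-response (telephone screening, a short survey, possible compensation) and on drawing from all current users whatever quantity they were supplied. It then closes: "These limitations are acknowledged and, given the nature of the data collected, should not greatly impact the conclusions drawn from the data collected from respondents".

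The parts of the plan that bear on this are:

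- **Target (9.1):** "The researchers will secure responses from 55 individuals from the four selected countries".
- **Response (9.5):** "Taking into account response rate of roughly 60 % and screening failures an estimated 120 surgeons will be screened for eligibility". Further countries may be added if recruitment falls short, and completed surveys above target are also analysed.
- **Contact (9.2):** the sample is a convenience sample. Hospitals come from sales records. "During the initial phone call, screening questions will be asked to determine the eligibility of the physician for participation". Eligible surgeons get a personal link, up to two reminders, and a call with the second.
- **Analysis (9.7):** only screened, eligible surgeons who completed the questionnaire count. Exploratory and sensitivity analyses are optional and look for differences between groups of responders. The measures are judged effective at 80 % aware, stated as 44 of 55.
- **Checklist (Annex 2, section 10):** missing data are marked not applicable because only completed questionnaires enter. Sensitivity analyses are marked as described in 9.7.
- **Descriptive items (9.3, Annex 3):** specialty, practice type, years of use and number of InductOs patients are listed as questionnaire items.

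**The concern.** The verdict is one proportion set against a fixed pass mark. The bias that 9.10 names pushes that proportion up, towards passing. The only reason given for discounting it is the nature of the data. A knowledge score has no property that protects it from self-selection: engaged surgeons are both more likely to answer and more likely to know the material.

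The planned response rate leaves a large share of eligible surgeons unobserved, and the protocol plans no description of them. Followed as written, the plan would let a borderline pass among completers stand as an unqualified finding that the educational materials work. The goal in section 8 concerns spine surgeons who use InductOs, not only those who answer. Timing matters too: a later SAP can add tables, but it cannot recover items that were not noted at the screening call.

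**Working it through.** **Inputs from the protocol.** 9.5: "an alfa of 0.05 with a two-sided interval and a distance from proportion to limit of 0.1 was used", "with the expected proportion of 90" %, 55 completed surveys, about 60 % response, 120 screened. 9.7: pass at 44 of 55.

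**1. Reproduce the plan's own figures.** n = 1.96² × 0.90 × 0.10 / 0.10² = 34.57, rounded up to 35. This agrees with 9.5: "This leads to a minimum sample size of 35". Also 0.80 × 55 = 44, as in 9.7. Both figures deal with sampling error only; neither allows for non-response bias.

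**2. Unobserved surgeons.** Assume the 60 % applies to eligible invited surgeons. Invitations needed are 55 / 0.60 = 91.7, about 92, which leaves 92 − 55 = 37 non-completers. Then 92 / 120 = 77 % of those screened would be eligible, which fits the planned 120.

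**3. A borderline pass carried to all 92.** Let q be awareness among non-completers. The documents do not give it, so it is assumed. Overall awareness = (44 + 37q) / 92.

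| q | Overall awareness |
|---|---|
| 0.70 | 69.9 / 92 = 76 % |
| 0.60 | 66.2 / 92 = 72 % |
| 0.50 | 62.5 / 92 = 68 % |
| 0.40 | 58.8 / 92 = 64 % |
| 0 (lower bound) | 44 / 92 = 48 % |
| 1 (upper bound) | 81 / 92 = 88 % |

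For q from 0.70 to 0.40 the shift is 4 to 16 points, against the 10-point distance on which the sample size rests.

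**4. A comfortable pass.** If 90 % of responders are aware, the planning value, overall awareness is 0.60 × 0.90 + 0.40q. It falls below 80 % once q < (0.80 − 0.54) / 0.40 = 0.65.

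**5. Chance of passing under assumed selection.** Overall response is held at 60 % and the tail is exact binomial with n = 55.

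- True awareness 70 %, no selection: P(44 or more) = 6.7 %. If aware surgeons respond at 70 %, unaware ones respond at (0.60 − 0.70 × 0.70) / 0.30 = 37 %. Awareness among responders is 0.49 / 0.60 = 82 %, and P = 70 %.
- True awareness 75 %, no selection: P = 24.6 %. If aware surgeons respond at 65 %, unaware ones respond at (0.60 − 0.75 × 0.65) / 0.25 = 45 %. Awareness among responders is 81 %, and P = 67 %.

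The differential response rates are assumptions. They show that moderate selection is enough to reverse the verdict.

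**The case against.** - **The closing sentence of 9.10 is limited to conclusions from respondents' data, and the bias is openly disclosed.** This is partly right. 9.7 does define the pass mark on respondents, 9.2 calls the sample a convenience sample, and section 7 records that careful interpretation was expected. But the conclusion to be drawn is that the measures are effective, which is not worded as a statement about respondents only.
- **The plan works to reduce non-response.** It does, through compensation, a short survey, two reminders and a call. These may raise response, but the planning figure is still about 60 %, and none of them shows whether bias remains.
- **Disposition tables and scenarios belong in a SAP or report.** Often so, and their absence alone would not be a point. The unsupported sentence is protocol text, however, and items not captured at the call cannot be added later.
- **The 60 % has no stated denominator.** Correct. If it applies to all 120 screened, 72 respond and 48 do not, some of them ineligible or never reached by phone. The 92 and 37 are therefore conditional.
- **Comparing characteristics does not reveal awareness, and the groups are small.** Correct. With 55 versus 37 and proportions near 50 %, the standard error is √(0.25/55 + 0.25/37) = 0.106, so 80 % power needs a difference of about 2.8 × 0.106 = 30 points. A lack of difference would prove little.

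Two stronger readings are tempting and are not supported. A reader might infer that non-completers are replaced until 55 surveys are in. The protocol has no replacement rule and does not stop at 55; it over-screens towards a target. A reader might also infer that nothing is known about non-completers, so that bias cannot be detected. Sales records, personal links and the unique logins in 9.6 mean that country and hospital are known for invitees, and the screening script is not shown. What can be said is that the protocol plans no use of such information.

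**Conclusion.** The point holds as a mismatch between the reassurance in 9.10 and the rest of the plan. The protocol names a bias with a direction, expects about 40 % non-response, restricts analysis to completers, and then discounts the bias without evidence. A pass at exactly 44/55 would be compatible with 64 % to 76 % awareness overall for assumed non-completer awareness of 40 % to 70 %, provided the 60 % applies to eligible invited surgeons. The 48 % to 88 % bounds need no assumption about non-completer awareness, only that reading of the 60 %.

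None of this shows that bias will occur or how large it will be. It shows that a plausible amount could decide the verdict, so the statement that the conclusions are not greatly affected cannot stand as written.

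**What to change.** 1. **9.2:** keep country and hospital type, already known from recruitment, for every eligible surgeon. At the screening call, also record specialty and the approximate number of InductOs patients in the past 2 years. Cover these items in the privacy notice, since some surgeons will never reach survey consent.
2. **9.7:** tabulate approached, eligible, invited and completed by country. Describe completers and non-completers on these items, and state that a lack of difference is not proof of no bias. Show the awareness proportion over a stated range of non-completer awareness, for example 40 % to 80 %.
3. **9.10:** replace the closing reassurance with a statement that the proportion may be biased upwards and that the 80 % verdict applies to respondents.

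The cost is a slightly longer call, a line in the privacy notice, some extra tabulation and a more cautious conclusion. Sample size and questionnaire are unchanged. Item 1 has to be in place before the screening calls begin.

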# 9.11 Other aspects

Not applicable.

# 10. Protection of human subjects

Any regulatory required ethics assessment or permissions will be obtained prior to the study start.

# **Participant Information and Consent**

The participants will receive a thorough briefing on the nature and purpose of the study to enable and inform their consent decision, see the questionnaire in Annex 3. Their consent will be recorded.

#### **Personal Data**

Following the implementation of the General Data Protection Regulations (GDPR) participants will be required to demonstrate that they agree to the completion of the survey. Participants (data subjects) will be informed of the data processing activities using their data, and organisations who may require access under what conditions. Privacy notices will set out how personal information is used and what the data subjects' rights are.

The research participant will be allowed to withdraw their consent for use of their personal information at any time regardless of any implications for the research project.

## **Confidentiality**

Every effort will be made to protect participant confidentiality. Participant identifiers will not be disseminated or placed on any reports generated by this study. Analyses will be conducted with anonymized data. Unless authorized by the participant (for example, in the case of an AE or product complaint report), only anonymized data will be made available to Medtronic BioPharma in accordance with privacy protection rules as dictated by applicable regulations.

The researchers will abide by any and all appropriate laws and codes related to their activities.

# 11. Management and reporting of adverse events/adverse reactions

This study does not involve data collection on clinical outcomes of individual patients. However, any information with regards to adverse events or product complaints voluntarily offered by a participant during the course of this study will be handled as described below.

Suazio's employees performing the screening interviews and the initial data analysis are trained to recognize adverse events and product complaints per Suazio's procedure. For this study any noted adverse event or product complaint will be reported on a Product Information Report (PIR, see Annex 1) and sent to Medtronic BioPharma's designated contact. The reported information will be further processed as per local requirements and Medtronic BioPharma's procedures. Suazio may be asked to support in requesting follow-up information.

# 12. Plans for disseminating and communicating study results

The final study report will be published via the EU PAS register and provided to the EMA and to the local Competent Authorities as relevant.

# Annex 1. List of stand-alone documents

Number	Document reference number	Date	Title
1	500231	01 May 2019	Product Information report

Study title:

6

# Annex 2. ENCePP checklist for study protocols ENCePP Checklist for Study Protocols (Revision 4)

Adopted by the ENCePP Steering Group on 15/10/2018

The European Network of Centres for Pharmacoepidemiology and Pharmacovigilance (ENCePP) welcomes innovative designs and new methods of research. This Checklist has been developed by ENCePP to stimulate consideration of important principles when designing and writing a pharmacoepidemiological or pharmacovigilance study protocol. The Checklist is intended to promote the quality of such studies, not their uniformity. The user is also referred to the ENCePP Guide on Methodological Standards in Pharmacoepidemiology, which reviews and gives direct electronic access to guidance for research in pharmacoepidemiology and pharmacovigilance.

For each question of the Checklist, the investigator should indicate whether or not it has been addressed in the study protocol. If the answer is "Yes", the section number of the protocol where this issue has been discussed should be specified. It is possible that some questions do not apply to a particular study (for example, in the case of an innovative study design). In this case, the answer 'N/A' (Not Applicable) can be checked and the "Comments" field included for each section should be used to explain why. The "Comments" field can also be used to elaborate on a "No" answer.

This Checklist should be included as an Annex by marketing authorisation holders when submitting the protocol of a non-interventional post-authorisation safety study (PASS) to a regulatory authority (see the Guidance on the format and content of the protocol of non-interventional post-authorisation safety studies). The Checklist is a supporting document and does not replace the format of the protocol for PASS presented in the Guidance and Module VIII of the Good pharmacovigilance practices (GVP).

	EU PAS Register® number: EUPAS32916 Study reference number (if applicable): N/A						
Stut	ry reference number (if applicable). WA						
Sect	ion 1: Milestones	Yes	No	N/A	Section Number		
1.1	Does the protocol specify timelines for						
	1.1.1 Start of data collection 				6		
	1.1.2 End of data collection 				6		
	1.1.3 Progress report(s)						
	1.1.4 Interim report(s)			$\boxtimes$			

 $\boxtimes$ 

1.1.5 Registration in the EU PAS Register®

1.1.6 Final report of study results.

<sup>1 Date from which information on the first study is first recorded in the study dataset or, in the case of secondary use of data, the date from which data extraction starts.

<sup>2 Date from which the analytical dataset is completely available.

#### Comments:

Given the short planned duration of the study, there are no progress or interim reports foreseen.

Sect	tion 2: Research question	Yes	No	N/ A	Section Number
2.1	Does the formulation of the research question and objectives clearly explain:				
	2.1.1 Why the study is conducted? (e.g. to address an important public health concern, a risk identified in the risk management plan, an emerging safety issue)				7
	2.1.2 The objective(s) of the study?				8
	2.1.3 The target population? (i.e. population or subgroup to whom the study results are intended to be generalised)				9.2
	2.1.4 Which hypothesis(-es) is (are) to be tested?		$\boxtimes$		
	2.1.5 If applicable, that there is no a priori hypothesis?				

#### Comments:

This study is set up to measure the awareness of surgeons at the time of the study. There is no hypothesis set to be tested.

Sect	tion 3: Study design	Yes	No	N/ A	Section Number
3.1	Is the study design described? (e.g. cohort, case-control, cross-sectional, other design)				9.1
3.2	Does the protocol specify whether the study is based on primary, secondary or combined data collection?				9.1, 9.3
3.3	Does the protocol specify measures of occurrence? (e.g., rate, risk, prevalence)		$\boxtimes$		
3.4	Does the protocol specify measure(s) of association? (e.g. risk, odds ratio, excess risk, rate ratio, hazard ratio, risk/rate difference, number needed to harm (NNH))		$\boxtimes$		
3.5	Does the protocol describe the approach for the collection and reporting of adverse events/adverse reactions? (e.g. adverse events that will not be collected in case of primary data collection)				11

#### Comments:

This study doesn't study a particular disease or risk factor. The study examines the awareness of information of surgeons at the time of the study. Therefore no measures of occurrence or association are collected.

Sect	ion 4: Source and study populations	Yes	No	N/ A	Section Number
4.1	Is the source population described?				9.2
4.2	Is the planned study population defined in terms of:				
	4.2.1 Study time period				9.2
	4.2.2 Age and sex				
	4.2.3 Country of origin				9.2, 9.5
	4.2.4 Disease/indication				9.3
	4.2.5 Duration of follow-up				
4.3	Does the protocol define how the study population will be sampled from the source population? (e.g. event or inclusion/exclusion criteria)				9.2

#### Comments:

There is no difference made for the inclusion in this based on age or sex as this is not relevant for the research questions and objective.

This is a cross-sectional study; hence the duration of follow-up is not defined.

	ion 5: Exposure definition and surement	Yes	No	N/ A	Section Number
5.1	Does the protocol describe how the study exposure is defined and measured? (e.g. operational details for defining and categorising exposure, measurement of dose and duration of drug exposure)			$\boxtimes$	
5.2	Does the protocol address the validity of the exposure measurement? (e.g. precision, accuracy, use of validation sub-study)			$\boxtimes$	
5.3	Is exposure categorised according to time windows?			$\boxtimes$	
5.4	Is intensity of exposure addressed? (e.g. dose, duration)			$\boxtimes$	
5.5	Is exposure categorised based on biological mechanism of action and taking into account the pharmacokinetics and pharmacodynamics of the drug?				
5.6	Is (are) (an) appropriate comparator(s) identified?			$\boxtimes$	

